The general study enrollment and investigational plan for Year # 1 (2020) and Year # 2 (2021) is illustrated and outlined in Figure 1 and Figure 2 respectively. Details regarding each individual study visit are illustrated and outlined in Figures 3-7. The study visits and details regarding each visit are further detailed in section 10 “Study Visits”.

The study PI and other investigators will be blinded to the allocation of participants to either carnosine or placebo. The participants will also be blinded to their allocation. The Randomization Committee (RC) will be in possession of the randomization key so that accurate unblinding of the randomization assignment may be identified in the event of a medical or other Carnosine NEAT Trial Protocol
Version Date 5-14-2020

emergency. The RC will consist of four individuals: the pharmacist compounding the supplement ([name]), the study physician ([name]), a member of the UofL Clinical Trials Unit, and the study biostatistician ([name]). Study supplements (carnosine or placebo) will be prepackaged into punch cards and marked with letters "A" or "B". The contents of series "A" or "B" will be part of the blinded randomization and will be known only to the RC. The study supplements will be directly shipped, stored and handled by the UofL CTU.

An initial screening (Visit # 1) of potential / interested participants will be conducted to identify eligible candidates based on eligibility criteria established *a priori*. Eligible candidates will be invited to a complete baseline assessment (Visit # 2). Randomization and allocation will occur between Visit # 1 and Visit # 2. Participants invited for Visit # 2 will already be randomized into one of the two study groups (carnosine or placebo). Participants from both study groups will be followed up at 6 weeks (Visit # 3) and 12 weeks (Visit # 4). Relevant and extensive data for primary and secondary endpoints will be collected at Visit # 2 through Visit # 4. The data collected throughout all visits (# 1 through # 4) may be used to generate preliminary data for future studies.

Visit # 1 will focus on consenting the participant for the entire study, collect contact/demographic information, and collect a urine sample. Safety assessments will be conducted at Visit # 3 and Visit # 4. Participants may be contacted for up to 12 months after enrollment via phone/email/mail for safety, adverse events, and or general follow up questions.

Study Endpoints

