All participants enrolled in this clinical trial will be identified as males or females, age 22-65, living within 30 miles radius of Louisville metropolitan area, and with carnosine levels less than the median of local population. After being identified (from existing database, from clinics, flyers, or other routes), potential participants will be approached by one of the investigators or research coordinators. The information provided to the potential participant is included in the informed consent. The informed consent will provide information regarding PM_{2.5} pollution, prevalence of PM_{2.5} pollution in the study area, synthesis and natural role of carnosine in the body, natural and supplemental sources of carnosine, cornstarch (constituent of placebo), and will include information regarding possible risks of participation.

Randomization

Eligible participants identified from Screening (Visit # 1) will be randomized in to supplement or placebo groups by 1:1 distribution. Randomization will be performed in accordance with written standard operating procedures by personnel that are not involved in the selection, screening, or enrollment of subjects and blinded as to study documentation. Randomization to supplement assignment will be conducted using a web access database created and maintained by the Randomization Unit. After the investigator or research coordinator verifies that screening testing is complete and the inclusion and exclusion criteria for the study have been satisfied, an un-blinded member of the Randomization Unit will have secured access to the participant's supplement assignment. The participant will be randomized a minimum of 2 days before the scheduled date of the baseline assessment (Visit # 2) to arrange for the timely availability of the study supplement. See Manual of Operations for details

Stopping Early or Withdrawal from the Study

Monitoring rules and statistical boundaries for adverse outcomes are further detailed in Section 15 "Data and Safety Monitoring Board". Below is the outline for recusal or withdrawal of participant from the study due to a non-health / safety related reason.

[figure not shown]
Participants that have consumed study supplement for at least 4 weeks during the duration of the study period, but missed taking the study supplement for no more than 1 week during the study period will still be followed if feasible, and included in intent to treat analysis.

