Blinding of the study personnel recruiting the participants and giving the pill-boxes will be facilitated by the fact that all study participants (Carnosine and placebo) will receive a dietary supplement. All study dietary supplements will be matched in color, consistency, and taste. The primary and secondary endpoints of the study will be determined by core laboratories whose personnel are blinded to supplementation assignment. In addition, the study recruitment and regulatory teams will take steps to ensure that endpoint and adverse event assessments are carried out in a blinded fashion.

Should unblinding occur, the Executive Committee consisting of the study PI, the study physician, and UofL CTU will be informed about the circumstances and they will discuss the circumstances related to the unblinding and further course of action. Any instance of unblinding will be documented in the study database and will be reported to the IRB as required.

Study Supplement Requirements

Study Supplement Packaging and Labeling

Study supplement packaging and labeling will meet all local and federal requirements. Study supplement (carnosine and placebo) label includes the product number, letter "A" or "B", volume, expiration date and time, storage conditions, and contact name and address. All supplements will be labeled for investigational use only.

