Supplement capsules will be pre-sorted into monthly (28 day) pill boxes by the unblinded laboratory personnel at the University of Colorado, Skaggs School of Pharmacy and Pharmaceutical Sciences. Pre-sorted pill boxes will be created for a total of 12 weeks per participant. The University of Colorado, Skaggs School of Pharmacy and Pharmaceutical Sciences personnel will label each box clearly as letter "A" or letter "B", indicating whether the box contains Carnosine or placebo supplement. The study personnel at the University of Louisville involved in recruitment, processing, analysis, or any other direct participant contact will be blinded to whether "A" boxes contain Carnosine or placebo, and similarly whether "B" boxes contain Carnosine or placebo. The University of Colorado, Skaggs School of Pharmacy and Pharmaceutical Sciences personnel will ensure that there is absolute consistency in the contents of each series of labeled boxes. The University of Colorado Skaggs School of Pharmacy and Pharmaceutical Sciences will ensure that the contents of each box are not disclosed to anyone involved with the study (staff, investigator, or participant) and will directly and securely send the randomization key to the Randomization Committee (study physician and UofL CTU).

Study Supplement Storage Requirements

L-Carnosine is tested on arrival to establish its purity and retested about every 6-12 months. L-Carnosine receives a three-year dating each time it passes re-assay. Product is stored at controlled room temperature. A sample of packed capsules will be retained, which will be re-assayed about every six months. Potency and stability testing services will be provided using Nuclear Magnetic Resonance and Liquid Chromatography/Mass Spectrometry in the Medicinal Chemistry Core Facility of the University of Colorado, Skaggs School of Pharmacy and Pharmaceutical Sciences.

United States Pharmacopeia (USP) <795> allows 180 day dating for compounded capsules, with extension of dating with ongoing stability studies. Initial potency and purity are established using Nuclear Magnetic Resonance and Liquid Chromatography/Mass

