The DSMB will use a combination of, notifications, event specific reports, and scheduled cumulative trial reports to keep the EC and the IRB informed about real and potential safety issues.

Notifications

Notifications are comprised of an email to the EC and DSMB with available information on the date and nature of the event, the study physician’s evaluation of the severity, expectedness, and relatedness to study supplement; and the assessment of the event given the information known at the time of the initial reporting.

Event Specific Reports

Event specific reports are formal written reports providing the details of the event (including circumstances surrounding the event, laboratory testing, concomitant medications, and any formal diagnoses made via medical intervention). These reports include a full assessment by

the study physician of the severity, expectedness, and relatedness to study supplement as well as any available status update on the participants.

Scheduled Cumulative Trial Reports

Scheduled cumulative trial reports will be prepared semi-annually by the study PI. These will be used by the DSMB to assess recruitment, subject safety, and continued trial feasibility. These reports include total numbers of AE/SARs and SAE/SSARs experienced in the overall trial. The information provided includes both new events reported since the last DSMB meeting and cumulative events reported during the life of the trial.

CTU Reporting Requirements to DSMB and IRB

Once the event has been reported to the PI or the study physician, it will be reported to the Executive Committee within 48 hours. The UofL CTU (part of the EC) will use the Medical Dictionary for Regulatory Activities (MedDRA) System Organ Classes (SOC) to classify all AEs/SARs (including SAEs/SSARs assessed by PI or study physician). Additional supporting documentation may be requested from the PI and study team to enable the UofL CTU to accurately assess the event for reporting.

Reportable Events:

All unexpected events, all events related to study product, and all events with a severity grade of 3 or higher are reported by the UofL to the DSMB and the IRB.

Reporting Timeframe:

[figure not shown]
For events which are unexpected AND associated with study supplement, the CTU will notify the IRB and DSMB within 72 hours of learning of the event; with an event specific report filed no later than 7 days post notification.

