15. STATISTICAL PROCEDURES

Randomization

Randomization to Carnosine assignment will be conducted using a statistical software by one of the study statisticians. The randomization key detailing which participant is in which group (Carnosine or placebo) will be maintained by the Randomization Committee (RC) consisting of the study physician ([name]) and a member of the UofL CTU. After the investigator or research coordinator verifies that screening testing is complete and the inclusion and exclusion criteria for the study have been satisfied, an un-blinded member of the Randomization Committee will have secured access to the participant's supplement assignment.

Participants will be randomized to the Carnosine or placebo group, using a block size of 6. The stratification factors are sex, age (two group) and carnosine level (two group). When a participant is identified from the screening process (data from Visit # 1), the clinical recruitment team will be informed whether the participant will be receiving supplements from pill-box labeled "A" or "B. The clinical recruitment team will assign the participant a study ID from a pre-defined series, which will have no bearings on supplement randomization process.

As detailed in Section 11 "Study Supplement", the University of Colorado Skaggs School of Pharmacy and Pharmaceutical Sciences will ship 28-day pill-boxes (total 3 per participant) pre-filled with either Carnosine or placebo. These boxes will also be pre-labeled with large sized visible letters "A" or "B". The entire study team, excluding the Randomization Committee, will be blinded to whether "A" or "B" series contains Carnosine versus placebo. The University of Colorado, Skaggs School of Pharmacy and Pharmaceutical Sciences personnel will ensure that there is absolute consistency in the contents of each series of labeled boxes. The University of Colorado Skaggs School of Pharmacy and Pharmaceutical Sciences will directly and securely transmit the randomization key and other relevant information to the Randomization Committee (study physician and UofL CTU).

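### The study physician holds the randomization key and also rates adverse events, and the protocol states no barrier between the two roles despite promising blinded assessment

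*Combined protocol and SAP*

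**What the plan says.** **Who holds the key.** Section 15 (Randomization) describes a key giving each participant's group, which "will be maintained by the Randomization Committee (RC) consisting of the study physician" and a member of the CTU. It then sets the limits of the blind: "The entire study team, excluding the Randomization Committee, will be blinded to whether" the A or B series is carnosine. Section 8 (Study Design) gives a longer list: "The RC will consist of four individuals: the pharmacist compounding the supplement", then the study physician, a CTU member and the study biostatistician. It says the committee is "in possession of the randomization key so that accurate unblinding of the randomization assignment may be identified" in an emergency. In Section 11 (Study Supplement Packaging and Labeling) the pharmacy "will directly and securely send the randomization key to the Randomization Committee (study physician and UofL CTU"). Section 9 (Randomization) uses another name and lists no members: "Randomization to supplement assignment will be conducted using a web access database created and maintained by the Randomization Unit". It refers to a Manual of Operations for details.

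**Who rates adverse events.** Under Section 14 (Notifications), the emails to the Executive Committee and the DSMB carry the study physician's "evaluation of the severity, expectedness, and relatedness to study supplement; and the assessment of the event given the information known" at first reporting. Event Specific Reports contain a full assessment by the physician on the same three attributes. The physician also takes part in restart discussions (Section 9, Medical or Health Concerns) and in continue/discontinue review with the DSMB (Section 10, Safety Evaluations), and makes an assessment with recommendations to the PI (Section 16, Consuming Dietary Supplement).

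**What is promised.** Under Section 11 (Randomization and Blinding), the recruitment and regulatory teams will take steps to "ensure that endpoint and adverse event assessments are carried out in a blinded fashion".

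**The concern.** Expectedness and relatedness are judgements. A rater who knows the arm may call the same event expected under carnosine and unexpected under placebo, or the reverse, without meaning to. The same applies to advice on restarting or continuing the supplement. Those ratings accompany the event to the DSMB and the IRB, and under Section 14 they bear on how quickly each body hears of it. If the person making them knows the arm, the safety comparison loses the protection that Section 11 promises, and the trial report could not describe adverse-event assessment as blinded without qualification.

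**Working it through.** The plan gives no figure to reproduce. The check sets the sections side by side.

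1. **Is the physician outside the blind?** Four places describe who handles allocation: Sections 8, 9, 11 and 15. Three of them (8, 11, 15) name the physician as a key holder; Section 9 names no one. Section 8 confines knowledge of the A/B contents to the committee, and Section 15 makes the committee the exception to the blind. On the text, the physician is unblinded.

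2. **Is any barrier stated?** Section 8 gives emergency unblinding as the purpose of holding the key. Sections 9 and 15 mention secured access by an unblinded member once eligibility is confirmed. Neither statement seals the key from the physician, limits the physician to on-request access, or names a separate blinded rater.

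3. **Which ratings keep a blinded rater?** The PI is blinded (Section 8).

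| Attribute | Study physician (Section 14) | Blinded PI (Section 13) |
|---|---|---|
| Severity | yes | yes |
| Causality / relatedness | yes | yes, category recorded on the eCRF |
| Expectedness | yes | not assigned |

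4. **Does the CTU close the gap?** Section 14 has the CTU classify events and assess them for reporting. But a CTU member holds the key (Sections 8 and 15), and CTU staff keep accountability logs that contain unblinded information (Section 11, Study Supplement Accountability). The text does not say that these are different people, so the CTU has a related overlap.

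5. **What can an expectedness call change?** Section 14 (Reportable Events; Reporting Timeframe) gives three routes. Unexpected and related: notice within 72 hours. Otherwise, if unexpected, or related, or grade 3 or higher: within 15 days. None of these: the semi-annual cumulative report only. Holding grade and relatedness fixed:

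| Grade | Related? | If unexpected | If expected |
|---|---|---|---|
| below 3 | yes | 72 hours | 15 days |
| below 3 | no | 15 days | semi-annual only |
| 3 or higher | yes | 72 hours | 15 days |
| 3 or higher | no | 15 days | 15 days |

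Two qualifications apply. Grade 1 events are not entered in the eCRF (Section 13, Severity Assessment), so the first two rows concern mainly grade 2. Section 14 (Guidelines for Canceling Study Supplement Administration) also puts gastrointestinal upset, sudden falls in blood pressure or blood sugar, and haemodynamic instability within 48 hours of planned consumption under the SAE/SSAR reporting criteria. How that rule interacts with the table is not stated. The table shows what the rules allow, not how often each row occurs.

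**The case against.** The strongest reply is that holding a key is not using it. Section 8 ties the key to emergencies, Section 9 cites written operating procedures and a Manual of Operations, and the promise in Section 11 is to take steps rather than a list of who is blind. Access controls may exist in papers that were not available. This stands as far as it goes: a reader might infer that the blind is broken in practice, and the documents do not show that. They show that the protocol text exempts the physician from the blind and states no firewall.

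A second reply is that the physician does not decide alone. That also stands in part. The PI rates severity and causality, an undetermined cause defaults to possibly related (Section 13), reported events reach the Executive Committee, which includes the PI, within 48 hours, and the CTU assesses events for reporting. A reader might infer that the physician's rating by itself sets the reporting route, or does so for most events. No section says the first. For the second, the plan gives no event mix with which to weight the rows of the table.

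A third reply is that the DSMB is unmasked by design (Section 14). That is true, and it means the Section 10 review is not fully blinded in any case. It does not remove the promise of blinded assessment made for the ratings that the DSMB receives.

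A reader might also take the fixed A and B letters as a further breach. The plan confines their meaning to the committee, so the letters do not contradict the blind and no relabelling is asked for.

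**Conclusion.** The concern holds as an unreconciled overlap of roles in the protocol text. The physician is a key holder outside the blind and a named rater of adverse events, blinded assessment is promised, and nothing written separates the roles. The exposure is narrowest for severity and causality, where a blinded PI also rates, and widest for expectedness, where the physician is the only individual rater named. The CTU's position is similar.

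The size of any bias cannot be estimated from the documents. It is bounded by the safeguards already in the plan: cumulative reports include all events, and the DSMB monitors the distribution of all serious events. The laboratories that determine the endpoints are blinded (Section 11), so bias in the EPC and other laboratory results is unlikely. The conclusion assumes that the Manual of Operations does not already impose the separation. If it does, the protocol should say so.

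**What to change.** - Remove the study physician from the key holders. Leave the key with the compounding pharmacist and one named CTU member who takes no part in classifying or assessing events, with a named backup. Keep the unblinded accountability logs apart from event work in the same way.
- Keep emergency access: the physician can obtain a single participant's assignment on request, with each unblinding documented as Section 11 (Randomization and Blinding) requires.
- State who rates expectedness, and whether the PI's causality category governs reporting.
- Use one name and one membership for the Randomization Committee or Unit in Sections 8, 9, 11 and 15, including whether the biostatistician listed only in Section 8 belongs to it. Reconcile these sections with the blinding promise and the accountability-log text in Section 11 and with the rating and reporting text in Section 14.

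The unmasked DSMB stays as planned. The cost is protocol wording, a named backup, one extra step when a code must be broken, and a separation of duties within the CTU, whose staffing is not stated. The pharmacist and a CTU member are already named as key holders in Section 8, so no new function is needed to hold the key.

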8. INVESTIGATIONAL PLAN

Research Questions

1. Does dietary supplementation of carnosine during a period of high PM_{2.5} pollution mitigate effects on vascular indices?
2. Does dietary supplementation of carnosine during a period of high PM_{2.5} pollution improve the arterial function?
3. Does dietary supplementation of carnosine during a period of high PM_{2.5} pollution decrease endothelial damage?
4. Does dietary supplementation of carnosine during a period of high PM_{2.5} pollution decrease platelet activation?

Study Design

This is a randomized, double-blind, placebo-controlled longitudinal clinical intervention study to assess whether dietary supplementation of a naturally occurring peptide in the body will mitigate the harmful effects of seasonal PM_{2.5} air pollution on indices of vascular biology. A total of 240 participants will be enrolled and randomized in 1:1 ratio to receive either dietary carnosine or placebo (cornstarch). Stratification factors are sex (birth male and female), age (22-44; 45-65) and carnosine level (very low, low). A block (or size 6) stratified randomization scheme will be used. Accounting for a conservative attrition rate of 40% (failure to complete all study time-points), a total of 400 participants will be randomized to receive either dietary carnosine supplementation or placebo (cornstarch).

The mode of dietary supplementation will be oral capsules. Intervention of dietary carnosine supplementation or placebo will occur daily, for 12 consecutive weeks during a period of high PM_{2.5} pollution – May through September. Due to logistical limitations, enrollment may be split over multiple years, but will occur during the same monthly period of high PM_{2.5} pollution (May through September) in the study region (30 miles radius from Louisville Kentucky). The 12 weeks supplementation period was selected based upon previous dietary carnosine supplementation trials as a reasonable and commonly used time frame to assess benefit and risk.^{34, 37} Based on existing literature, a measureable effect of carnosine on many indices is noticeable by 6 weeks of starting supplementation and can reach peak effect by 12 weeks.^{34, 37}

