Participants that withdraw from the study before Follow-Up # 1 (Visit # 3) or do not complete Visit # 3 will be considered lost to follow-up. Existing data of these participants will be retained for further analysis.

Screen Failure

Candidates are considered screen failures when they meet one of the following criteria after signing consent:

1. Screening (Visit # 1) data reveals that the candidate is ineligible
OR

2. Candidate withdraws and does not complete Baseline Assessment (Visit # 2)

Discontinued

Participants are considered discontinued when they meet one or more of the following criteria:

1. Participant withdraws consent after being randomized
OR
2. Participant withdraws consent after completion of Baseline Assessment (Visit # 2)
OR
3. Participant fails to follow study supplement regimen
OR
4. Participant is unable to fulfill the inclusion/exclusion criteria during the study
OR
5. Participant refuses/is unable to provide critical data at follow-up visits as deemed necessary by the investigator
OR
6. Participant is withdrawn after randomization by investigator for reasons that may compromise completion of the study

Medical or Health Concerns

Participants will be instructed that in an event of an acute health concern (related or unrelated to the study supplement), they should immediately discontinue the study supplement and seek medical attention from a licensed healthcare provider. Participants will be provided with a study identification card. This card will contain the following information: name of the study, name of study institution, a statement to the effect of *“each capsule may contain 0.5 grams of L-Carnosine or 0.5 grams of cornstarch”*, method of contacting the study physician, and a method of contacting the study coordinator.

Participants may be able to re-start supplement regimen and continue the randomization after detailed discussions with the study physician. The study physician may seek advisement from the DSMB on these matters.

Compensation

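### A fixed block size of 6, printed in the protocol, with each participant's A/B letter given to recruiters, makes up to a quarter of letters certain in advance if recruiters can follow all three strata

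*Combined protocol and SAP*

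**What the plan says.** - **Block size.** Section 8 (Study Design) says "A block (or size 6) stratified randomization scheme will be used", where the second word in the bracket is evidently a slip for *of*. Section 15 (Randomization) repeats it: "Participants will be randomized to the Carnosine or placebo group, using a block size of 6". Neither place mentions varying or concealed sizes.
- **Ratio and strata.** Allocation is 1:1, stratified by sex, two age groups and two carnosine levels (very low and low). The cut between the two levels is not defined.
- **Disclosure of the letter.** Section 15 says that, once a participant is identified from screening, "the clinical recruitment team will be informed whether the participant will be receiving supplements from pill-box labeled" A or B. The boxes carry the letter in large type.
- **One letter per arm.** Section 15 says the pharmacy's "personnel will ensure that there is absolute consistency in the contents of each series of labeled boxes". What A and B contain is withheld from the study team other than the Randomization Committee.
- **Timing.** Section 8 says "Randomization and allocation will occur between Visit # 1 and Visit # 2". Section 9 (Randomization) requires this at least 2 days before the baseline visit.
- **After allocation.** Section 10 (Baseline Assessment) allows exclusion if baseline data are incomplete or an exclusion criterion is met. Section 9 (Screen Failure) counts as a screen failure the case "Candidate withdraws and does not complete Baseline Assessment (Visit # 2". Section 9 (Discontinued) separately lists withdrawal of consent after randomisation.

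**The concern.** With two arm-wide letters, the letters already issued are the allocation sequence itself, up to a swap of labels. Anyone who sees them in order within a stratum, and knows the block size, can work out some of the coming letters. Matching the capsules does not prevent this.

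Two things are at stake. First, whether an allocated person goes on to complete Visit 2 could come to depend on the letter, and that would bias A versus B even if nobody knows which is carnosine. Section 9's exclusion criteria include an open-ended item on other medical conditions, so some discretion remains after allocation. Second, one correct inference about what a letter means, for example from tingling (a possible carnosine risk listed in Section 16), applies at once to every participant. Section 5 plans enrolment over 2020 and 2021, and no re-lettering between years is described. Second-year allocations could therefore be made after a full season of side effects had been seen by letter.

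**Working it through.** **Inputs.** Block size 6 and 1:1 allocation (Sections 8 and 15) give 3 A and 3 B per block. Three two-level factors (Section 8) give 2 × 2 × 2 = 8 strata. The number randomised is 400 (Sections 5 and 8).

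**The plan's own figure.** 240 / (1 − 0.40) = 400, which reproduces. The documents give no figure for predictability.

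**Certain letters in a complete block.** A letter is certain once the other has been used three times. For a block of 2m, the expected number of certain letters is 2m/(m + 1). With m = 3 this is 6/4 = 1.5 of 6, or 25%. Listing all C(6,3) = 20 orderings confirms it:

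| Certain letters in the block | Orderings | Probability |
|---|---|---|
| 1 | 12 | 0.60 |
| 2 | 6 | 0.30 |
| 3 | 2 | 0.10 |

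Mean: (12 × 1 + 6 × 2 + 2 × 3)/20 = 30/20 = 1.5. By position, the fourth letter is certain in 10% of blocks, the fifth in 40% and the sixth in all.

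**Best guess.** Always naming the letter with more left gives m + (2^(2m)/C(2m,m) − 1)/2 = 3 + (64/20 − 1)/2 = 4.1 correct of 6, or 68.3%.

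**Over the trial.** Assume equal strata: 400/8 = 50 each, which is 8 full blocks plus 2 letters. Certain letters per stratum: 8 × 1.5 + 0 = 12 of 50 (24%). Overall: 8 × 12 = 96 of 400.

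**If the carnosine level is hidden.** The recruiter then sees two interleaved block sequences without knowing which one each letter came from. A simulation that updates the probabilities after every letter, with the two levels equally common, gives about 0.6% certain and a best guess right about 63% of the time. A 70:30 split gives much the same.

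**Other block schemes.** These are simulated with 50 per stratum and all strata visible. The observer knows the set of sizes but not where blocks begin.

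| Scheme | Certain letters | Best guess correct |
|---|---|---|
| Fixed 6 | 24.0% | 68% |
| Random 4 or 6 | 5.6% | 69% |
| Random 4, 6 or 8 | 2.2% | 68% |

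Varying the size removes most of the certainty and almost none of the guessability.

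**The case against.** The strongest reply is that the 25% needs a recruiter who knows the carnosine stratum, and no section says recruiters are told it. The level comes from laboratory analysis of urine. This stands, and it is why the figure is an upper case. It does not settle the matter the other way: Sections 9 and 15 have the investigator or coordinator verify the entry criteria, which include carnosine below the median, and nothing says the finer level is withheld.

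Second, a letter of unknown meaning gives no motive to steer. This largely stands early on. Side effects are first reviewed at Visit 3, at least 5 weeks after baseline, while baselines run in May and June. Many 2020 allocations would precede any such review. Late-2020 and 2021 allocations would not have that protection.

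Third, consent for the whole study and eligibility come before randomisation, and Section 9 gives randomisation to personnel outside selection, screening and enrolment. This narrows the opening. A reader might infer that recruiters choose who is randomised next, because screening runs all year and eligible candidates may accumulate before May. No section says so, and the Manual of Operations to which Section 9 refers is not among the documents. The point does not rely on it.

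Fourth, a reader might infer that people lost after allocation disappear as screen failures. The documents do not settle this: someone who withdraws consent between randomisation and Visit 2 fits both the screen-failure and the discontinued definitions, and Section 15 requires reasons for discontinuation to be presented. The overlap is a separate question of definition, but it is a reason to count these losses openly.

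**Conclusion.** The concern holds in conditional form. The fixed size, its publication in the protocol and the disclosure of letters to recruiters are all stated. The consequence ranges from about 0.6% of letters certain and 63% guessable (carnosine level hidden and evenly split) to 25% certain and 68% guessable (all strata visible, complete blocks; 24% certain with 50 per stratum). The documents do not say which end applies.

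It would go too far to say that a quarter of treatment assignments are known in advance. The predictable item is the letter, and its meaning is held by the pharmacy and the Randomization Committee. Nor do the documents show that any selection would occur. This is a small, avoidable weakness in concealment. Sample size and power are unaffected.

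**What to change.** 1. Regenerate the list with randomly varying block sizes within strata, for example 4, 6 and 8. Take the size out of the protocol text and keep it in a document restricted to the Randomization Committee. The cost is close to nil. This deals with certainty (about 24% down to about 2%) but should not be presented as dealing with guessability.
2. To deal with guessability and the two-letter exposure as well, label boxes with participant-specific kit codes that carry no arm information, and give recruiters only the code. The cost is relabelling at the pharmacy and a code-to-arm list held by the Randomization Committee.
3. State in Section 15 that all losses and exclusions between randomisation and completion of Visit 2 will be reported by arm with reasons, whichever category in Section 9 they fall under. This needs no new data.
4. State whether recruiting staff are told the very low/low carnosine level. If they do not need it, withhold it.
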